Appendix 4. Calculation of Standard Body Weight

The following table will be used to determine the standard body weight for each subject. Height from the eCRF will be used and is assumed to be measured without shoes.

Women			
Height in cm (in shoes)*	Standard Weight in kg	Height in cm (in shoes)*	Standard Weight in kg
127	41.2	163	60.2
128	41.7	164	60.7
129	42.3	165	61.3
130	42.8	166	61.9
131	43.3	167	62.4
132	43.8	168	62.9
133	44.4	169	63.4
134	44.9	170	63.9
135	45.4	171	64.5
136	45.9	172	65.0
137	46.4	173	65.5
138	47.0	174	66.0
139	47.5	175	66.6
140	48.0	176	67.2
141	48.6	177	67.7
142	49.1	178	68.3
143	49.6	179	68.8
144	50.2	180	69.3
145	50.7	181	69.8
146	51.2	182	70.3
147	51.8	183	70.8
148	52.3	184	71.3
149	52.8	185	71.8
150	53.1	186	72.3
151	54.1	187	72.8
152	54.5	188	73.3
153	55.0	189	73.8
154	55.4	190	74.3
155	55.9	191	74.9
156	56.4	192	75.4
157	57.0	193	76.0
158	57.5	194	76.5
159	58.1	195	77.0
160	58.6	196	77.6
161	59.1	197	78.1
162	59.6	198	78.6

* add 2.0 cm if shoeless. Please round height to a whole number and select the appropriate standard weight (e.g., height 157.4 cm will be rounded to 157 cm; 157.5 cm will be rounded to 158 cm.)

Men			
Height in cm (in shoes)*	Standard Weight in kg	Height in cm (in shoes)*	Standard Weight in kg
142	54.4	179	71.9
143	54.9	180	72.4
144	55.4	181	73.0
145	55.8	182	73.6
146	56.3	183	74.3
147	56.8	184	74.8
148	57.2	185	75.5
149	57.7	186	76.2
150	58.2	187	76.9
151	58.6	188	77.6
152	59.1	189	78.2
153	59.6	190	78.8
154	60.0	191	79.6
155	60.5	192	80.4
156	61.0	193	81.2
157	61.4	194	82.1
158	61.9	195	82.9
159	62.2	196	83.8
160	62.6	197	84.7
161	62.9	198	85.4
162	63.3	199	86.1
163	63.7	200	86.7
164	64.1	201	87.4
165	64.6	202	88.0
166	65.0	203	88.8
167	65.5	204	89.4
168	66.0	205	90.1
169	66.6	206	90.7
170	67.1	207	91.4
171	67.6	208	92.1
172	68.1	209	92.7
173	68.7	210	93.4
174	69.2	211	94.1
175	69.7	212	94.8
176	70.3	213	95.5
177	70.8	214	96.1
178	71.3		

* add 2.0 cm if shoeless. Please round height to a whole number and select the appropriate standard weight (e.g., height 157.4 cm will be rounded to 157 cm; 157.5 cm will be rounded to 158 cm.)

Appendix 5. MaRIA (Magnetic Resonance Index of Activity) Scoring System

1) Component Details

Item	Definition	Sequence
Wall thickness (WT)	Maximum wall thickness (mm) of any portion of the segment will be the value for the segment.	T1 sequence after gadolinium injection. Perpendicular to bowel axis.
Relative Contrast Enhancement (RCE)	RCE accounts for enhancement in the intestinal wall using wall signal intensity (WSI) before and after contrast. Formula is noted below ^a ; SD is standard deviation.	T1 pre contrast, and T1 post contrast at 70 seconds.
Edema (E)	Hyperintensity on T2 wedged sequences of the colon wall relative to the signal of the psoas muscle. Edema may be a score of 0 (absent) or 1 (present).	Either single shot (SS) T2 or Balance gradient echo with fat saturation.
Ulcerations (U)	Areas of depression/irregularity in the inner surface of a thickened intestinal wall. Linear enhancing tracts within the bowel wall should be considered fissures (linear ulcers). Ulcerations may be a score of 0 (absent) or 1 (present).	All

a) RCE: $[(\text{WSI postgadolinium} - \text{WSI pregadolinium}) / \text{WSI pregadolinium}] \times (\text{SD pregadolinium} / \text{SD postgadolinium}) \times 100$

2) Segmental MaRIA Score Calculation

$$\text{Segmental MaRIA} = [1.5 * \text{WT(mm)}] + [0.02 * \text{RCE}] + [5 * \text{E}] + [10 * \text{U}]$$

Appendix 6. Study Treatment Failure Rules

Study treatment failure rules apply to treatment failure that occurs during the course of the study. Study treatment failure rules will be applied to all efficacy endpoints, unless otherwise specified. All efficacy data will be censored (set to missing) after treatment failure criteria are met, regardless of the observed data. Subjects who do not have sufficient measurements after censoring to determine the dichotomized endpoint(s) will be considered non-responder for corresponding endpoint(s). Study treatment failure rules override other data handling rules.

Subjects who have any of the following events will be considered a study treatment failure after the earliest event through the end of the Study, regardless of the actual efficacy data collected.

1) Potentially effective corticosteroid use

Potentially effective corticosteroids, for the purpose of this SAP, are corticosteroids that may impact disease under study. Potentially effective corticosteroids include the following corticosteroids when administered for an indication of CD:

a) Commencement of:

Any steroid administered intramuscularly (IM), intravenously (IV), orally (PO), or rectally (PR) at any dose for 7 or more continuous days

- This rule applies regardless if a change in drug, dose, or route (from IM to IV to PO or PR or vice versa) occurs within the seven continuous days; and it includes oral steroids with intended local actions (eg, budesonide)
- b) Escalation of concomitant steroid dose above the baseline dose for 7 or more continuous days. The baseline steroid dose is defined as the dose at Day 1 of the Study. The prednisone equivalent dose will be used to determine escalation of concomitant systemic steroid dose even if there is a change in drug or route. For steroids with local actions (eg, budesonide or any rectally administered steroid), this rule will apply to scenarios where the post-baseline dose is above the baseline dose via the same drug and the same route for 7 or more continuous days.

Potentially effective steroid use only includes use of steroids administered via routes that are IM, PO, IV, or PR. The below steroids will **not** be considered potentially effective steroids regardless of indication for use:

- A) ocular steroids (ie, eye drops)
- B) topical steroids (eg, cutaneously applied solely to the skin, or topically applied to the nasal mucosa)
- C) inhaled steroids (eg, inhalational fluticasone for asthma)
- D) intra-articular steroids (steroids administered directly into a joint)
- E) neuraxial steroids (steroids administered into the epidural or spinal space)

2) Potentially effective immunomodulator use

Commencement of a different class of oral, IM, SC, or IV immunomodulator drugs

(where the subject was not previously taking concomitant immunomodulators of the same class on Day 1), including but not limited to 6-MP, azathioprine, MTX, 6-thioguanine, and prohibited immunomodulators including but not limited to cyclosporine, leflunomide, tacrolimus, thalidomide regardless of dose, for 7 continuous days. The use of an immunomodulator will be considered potentially effective when it is administered for an indication of CD.

3) Potentially effective biologic agent use

Commencement of a biologic agent including but not limited to TNF α antagonists, IL-12/23 antagonists, and vedolizumab (or similar agents), regardless of indication for use and duration.

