#### **3.5. Criteria for Study Drug Interruption or Discontinuation**

##### **3.5.1. Study Drug Interruption Considerations**

The Gilead Medical Monitor should be consulted prior to study drug interruption when medically feasible.

Study drug interruption should be considered in the following circumstances; *prior to resumption of study drug, the investigator should discuss the case with the Gilead Medical Monitor:*

- Intercurrent illness that would, in the judgment of the investigator, affect assessments of clinical status to a significant degree
- Subject is scheduled for elective or emergency surgery (excluding minor skin procedures under local or no anesthesia); timing of study drug pausing should be determined in consultation with the Gilead Medical Monitor
- Any subject who develops a new infection during the study should undergo prompt and complete diagnostic testing appropriate for an immunocompromised individual, and the subject should be closely monitored

*NOTE: During the time of study drug interruption for any of the above, the subject may continue to have study visits and to take part in procedures and assessments, if deemed medically appropriate by the investigator.*

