#### **5.4.1. Allowed Concomitant Medications**

The allowed concomitant medication(s) for CD must be maintained at a stable dose for the noted time without dosing alteration or discontinuation. Subjects should not initiate new induction therapy prior to the screening visit. If a new therapy has been recently initiated, the full induction course should be completed prior to screening consideration.

The allowed medications for CD are as follows:

- Oral 5-ASA compounds provided the dose prescribed has been stable for at least 4 weeks prior to randomization; dose must be stable for the first 10 weeks after randomization
- Azathioprine, 6-MP, or MTX provided the dose prescribed has been stable for 4 weeks prior to randomization; dose must be stable for the first 10 weeks after randomization
- Oral corticosteroid therapy (prednisone prescribed at a stable dose of  $\leq$  30 mg/day or budesonide prescribed at a stable dose of  $\leq$  9 mg/day) provided the dose prescribed has been stable for 4 weeks prior to randomization; dose must be stable for the first 10 weeks after randomization
- Antibiotics for the treatment of CD (eg, metronidazole, ciprofloxacin) provided the dose prescribed has been stable for 2 weeks prior to randomization. Dose must remain stable for the first 10 weeks after randomization. Subjects who are on cyclic therapy must continue their standard low-dose regimen without change for the first 10 weeks after randomization
- Antidiarrheals for chronic diarrhea are allowed throughout the study as necessary for control of chronic diarrhea; stable doses are encouraged
- Occasional use of non-steroidal anti-inflammatory drugs (NSAIDs) for transient symptoms is permitted; daily use of aspirin up to 162.5 mg for the purpose of cardiovascular prophylaxis is permitted

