a May decrease study drug exposure and are excluded to avoid potential reduction in study drug activity. PK results indicate that filgotinib is a P gp substrate, as a single dose of 200 mg itraconazole (a potent P gp inhibitor) increased filgotinib Cmax by 64% and AUCinf by 45% and had no effect on the major, active metabolite GS 829845

b Occasional use of NSAIDs for transient symptoms and daily use of aspirin up to 162.5 mg for the purpose of cardiovascular prophylaxis are permitted.

c Other biologics may be allowed with the approval of the medical monitor.

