1.3. Sample Size and Power

A sample size of 40 subjects in each of the filgotinib treatment groups and 20 subjects in the placebo group is considered adequate to assess the safety, tolerability, and efficacy of filgotinib in a descriptive manner. Assuming a clinical remission rate of 40% for the filgotinib treatment groups (200 mg and 100 mg), the 2-sided 90% exact confidence interval is (26.9%, 54.2%). The clinical remission rate for placebo group is assumed to be 20%.

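### SAP Appendix 6 does not count same-class immunomodulator escalation or CD-related intestinal surgery as treatment failure, and rule 3 read literally fails a non-IBD biologic that the protocol may allow

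*SAP*

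**What the plan says.** SAP Appendix 6 defines treatment failure by a list: "Subjects who have any of the following events will be considered a study treatment failure after the earliest event". The rules apply to all efficacy endpoints unless otherwise specified and override other data handling. Efficacy data after the event are set to missing. The list has three entries.

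- **Rule 1, steroids for CD.** Failure is either starting a steroid (1a) or raising a concomitant steroid above the Day 1 dose (1b), for 7 or more continuous days.
- **Rule 2, immunomodulators for CD.** The trigger is "Commencement of a different class of oral, IM, SC, or IV immunomodulator drugs", for 7 continuous days, where the subject was not already taking that class on Day 1. There is no dose-escalation limb.
- **Rule 3, biologics.** Starting a biologic is a failure "regardless of indication for use and duration".

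Protocol 5.4.1 says of azathioprine, 6-MP and MTX that the "dose must be stable for the first 10 weeks after randomization". It sets no stability requirement after that. Protocol 3.5.1 gives as a reason to consider interrupting study drug: "Subject is scheduled for elective or emergency surgery". In the SAP, CD surgery appears only as baseline history (5.2). Protocol Table 5-1 lists other biologics, with denosumab and trastuzumab as examples, as needing medical monitor consultation, and footnote c adds: "Other biologics may be allowed with the approval of the medical monitor".

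**The concern.** Appendix 6 removes outcomes that may owe something to another effective CD treatment. It does this for a steroid dose increase but not for an immunomodulator dose increase, and gives no reason for the difference. It is silent on intestinal surgery for CD. SAP 6.1 treats a subject as a non-responder only when measurements are insufficient, so a subject with an evaluable Week 24 CDAI below 150 after either event is reported as a remission on the assigned arm.

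Rule 3 errs the other way if taken at its word. Rules 1 and 2 are limited to use for CD and rule 3 is not. A subject who starts an approved non-IBD biologic before Week 24 would have later efficacy data set to missing and become a non-responder. For the MaRIA change endpoints, SAP 6.3.2 would then put the baseline score in place of the missing Week 24 score, giving a change of zero.

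At stake is the meaning of the primary estimate in a small trial, and the risk that individual cases are settled after unblinding.

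**Working it through.** **Inputs.** SAP 1.3 gives the arm sizes ("A sample size of 40 subjects in each of the filgotinib treatment groups and 20 subjects in the placebo group") and assumed remission rates of 40% on filgotinib and 20% on placebo. SAP 6.2.2 gives 90% intervals and no hypothesis test. The classification rules are in SAP 6.1 and Appendix 6.

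**1. The plan's own figure.** Two-sided 90% Clopper-Pearson interval with x = 0.40 × 40 = 16 and n = 40: lower limit = 5th percentile of Beta(16, 25) = 26.9%; upper limit = 95th percentile of Beta(17, 24) = 54.2%. This matches the stated (26.9%, 54.2%), and the point raised here does not affect it.

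**2. How each event is classified when the Week 24 CDAI is observed below 150.**

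| Event before Week 24 | Appendix 6 | Counted as |
|---|---|---|
| Steroid above Day 1 dose, 7+ days, for CD | rule 1b | failure |
| New class of immunomodulator, 7 days, for CD | rule 2 | failure |
| Higher dose of an immunomodulator taken on Day 1, for CD | not listed | remission |
| CD-related intestinal surgery | not listed | remission |
| Non-IBD biologic allowed under footnote c | rule 3, read literally | failure |

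**3. Do the discontinuation rules close the gap?** Protocol 3.4 takes Week 10 non-responders and subjects with disease worsening off blinded treatment. A responder needs, at any point up to Week 10, a fall of 70 points or a CDAI below 150. With a Week 10 value of X, worsening requires at least max(X + 100, 220) at 2 consecutive visits. At the upper eligibility limit, a subject who enters at 450 and is at 450 − 70 = 380 at Week 10 is a responder, and meets the worsening criterion only at 380 + 100 = 480. A subject can therefore remain on study drug with active disease. The rules narrow the gap but do not close it.

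**4. Size of one misclassified subject.** 1/40 = 2.5 points in a filgotinib arm; 1/20 = 5 points on placebo. For the difference D = pF − pP, use SE = √[pF(1 − pF)/40 + pP(1 − pP)/20] and D ± 1.645 × SE. The SAP names no interval method for the difference, so this Wald interval is an assumption. Planning case: SE = √(0.4 × 0.6/40 + 0.2 × 0.8/20) = √(0.006 + 0.008) = 0.1183, giving 20.0 ± 19.5 points.

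| Scenario | Filgotinib | Placebo | Difference (points) | Wald 90% CI |
|---|---|---|---|---|
| Planning case | 16/40 | 4/20 | 20.0 | 0.5 to 39.5 |
| One filgotinib remitter becomes a failure (surgery or escalation) | 15/40 | 4/20 | 17.5 | −1.9 to 36.9 |
| One placebo remitter becomes a failure (surgery or escalation) | 16/40 | 3/20 | 25.0 | 6.7 to 43.3 |
| One filgotinib subject restored (rule 3) | 17/40 | 4/20 | 22.5 | 3.0 to 42.0 |
| One placebo subject restored (rule 3) | 16/40 | 5/20 | 15.0 | −5.4 to 35.4 |

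With two subjects reclassified for surgery or escalation, the difference is 15.0 (14/40 vs 4/20) or 30.0 (16/40 vs 2/20). One or two subjects per arm is an assumed range. The Newcombe interval for the planning case is −1.3 to 36.8, so whether the lower limit lies above zero already depends on the method chosen. The shift in the estimate is the result to read here.

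**The case against.** **The events should be rare.** Protocol 4.3 excludes symptomatic or clinically significant strictures, fistulae, imminent surgery (criterion 14) and likely surgery (criterion 19), and the Protocol 3.4 rules remove many subjects whose disease is not controlled. This stands, and it limits how much the point matters. It does not say how to classify a case that occurs. A resected segment with no Week 24 MaRIA score is already a non-response for that segment (SAP 6.1.2), but a single missing segment is carried forward at subject level, and the CDAI endpoint has no such safeguard.

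**The asymmetry has a source.** Protocol 5.4.3 itself makes steroids above the baseline dose a failure and sets no equivalent for immunomodulators. Counting a permitted dose change as failure is a choice of estimand, not the repair of an error. That is fair. But the SAP already goes beyond Protocol 5.4.3 by failing new immunomodulator classes and biologics, so the boundary is the SAP's own and needs a reason.

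**Rule 3 can be read narrowly.** Its heading speaks of potentially effective use and its examples end with similar agents, so ignoring the indication could mean, say, a TNFα antagonist given for another disease. This also stands: rule 3 is ambiguous, not plainly wrong. However, its examples are expressly not exhaustive, and it does not refer to the list of CD biologics in SAP Appendix 2.

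A reader might also infer that Protocol 3.5.1 foresees Crohn's bowel surgery with study drug resumed. That provision covers surgery in general, and resumption is subject to discussion with the medical monitor. Nor does the 12-week regimen in inclusion criterion 9b show that the 14 weeks from Week 10 to Week 24 give an escalation time to work. The criterion describes a past trial at stated doses, not the speed of a dose increase. Even on that yardstick, only escalations by Week 12 (24 − 12) would qualify.

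**Conclusion.** The point holds as a modest one. As written, remission after same-class immunomodulator escalation or CD-related intestinal surgery is credited to the assigned arm, provided the Week 24 CDAI is evaluable and below 150. Rule 3, taken literally, conflicts with what Table 5-1 footnote c can allow. The size is 2.5 or 5 points per misclassified subject; no total can be given because the documents contain no event frequencies.

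A reader might infer that the gap pulls the difference toward zero because these events are likelier on placebo. Nothing in the documents supports that. A wrongly credited placebo remission understates the difference, a wrongly credited filgotinib remission overstates it, and rule 3 works in reverse. A shrinkage of 5 to 10 points would require 1 to 2 placebo remissions to be due to these events and none on filgotinib. With 0.20 × 20 = 4 expected placebo remitters, that is 25% to 50% of them, which no document supports.

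The analysis is descriptive, so the consequence is bias and ambiguity in the estimate, not type I error.

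**What to change.** Change Appendix 6 as follows. This concerns analysis classification only, not patient management.

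1. Add CD-related intestinal surgery as a failure event.
2. Add to rule 2, mirroring rule 1b, escalation of a same-class immunomodulator above the Day 1 dose for 7 or more continuous days for CD.
3. Limit rule 3 to biologics potentially effective in CD, whatever the indication: for example the Appendix 2 list, other TNFα, integrin or IL-12/23 antagonists, and similar agents. This reconciles it with Table 5-1 footnote c.

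The cost is about three sentences, and observed remission rates may be slightly lower. Concomitant medications, including changes of dose, are documented as collected (Protocol 5.4 and 9.1.5). No form for on-study procedures is described, and procedures are not themselves AEs (Protocol 7.1.1), so the sponsor must confirm where surgery will be recorded. The change belongs in the SAP before it is finalized; SAP section 1 requires any later change to be documented in the CSR.

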#### 5.4.3. Corticosteroid Tapering

Starting at Week 10, subjects who are on concomitant steroids must begin tapering steroid therapy. The dose should be reduced at a rate starting at 2.5 mg per week up to 5 mg per week (or equivalent taper if not prednisone) until the subject is no longer on steroids. Subjects who are on budesonide should have their daily dose reduced by 3 mg every 3 weeks until they are completely off steroids. For subjects undergoing taper, steroids may be increased or restarted at doses up to and including their baseline dose if return of symptoms is apparent. These subjects

will not be considered treatment failures. Subjects who need to restart or increase steroid treatment at a dose that exceeds their baseline dose of steroids (dose may not exceed 30 mg/day prednisone [or equivalent] or budesonide 9 mg/day) will be considered treatment failures for all clinical endpoints but will be permitted to remain in the study and continue to receive study drug.

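### For subjects on corticosteroids at Day 1 who taper from Week 10, SAP Appendix 6 departs from the steroid failure rule in Protocol 5.4.3, and SAP 6.5 does not declare it

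*SAP*

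**What the plan says.** **Protocol 5.4.3** sets a single test, based on dose, for subjects tapering from Week 10.

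- Up to baseline: "steroids may be increased or restarted at doses up to and including their baseline dose if return of symptoms is apparent". Of anyone who does this, the section states that they "will not be considered treatment failures".
- Above baseline: "Subjects who need to restart or increase steroid treatment at a dose that exceeds their baseline dose of steroids" (within the 30 mg prednisone or 9 mg budesonide cap) "will be considered treatment failures for all clinical endpoints but will be permitted to remain in the study and continue to receive study drug". No minimum duration is given.

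**SAP Appendix 6, item 1** uses two rules, both limited to steroids given for Crohn's disease.

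- Item 1a, commencement: "Any steroid administered intramuscularly (IM), intravenously (IV), orally (PO), or rectally (PR) at any dose for 7 or more continuous days". It adds "This rule applies regardless if a change in drug, dose, or route" within the seven days, and it names budesonide as included. It mentions neither Day 1 use nor the baseline dose.
- Item 1b, escalation: "Escalation of concomitant steroid dose above the baseline dose for 7 or more continuous days", where baseline is the Day 1 dose.

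Under Appendix 6, efficacy data after failure are set to missing whatever was observed, a binary endpoint that can then not be determined becomes non-response, and the failure rules take precedence over other data handling. SAP 6.5, which lists changes from the protocol's efficacy analyses, covers only MaRIA and small bowel disease status definitions.

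**The concern.** Steroid failure decides primary-endpoint status regardless of the observed CDAI, so the two documents should give the same answer for the same subject. They do not, and they differ in both directions. A short course above baseline is a failure under the protocol but can pass under 1b. The protocol keeps that subject on study drug, so an observed Week 24 CDAI below 150 can exist, and the SAP would count it. A restart at or below baseline after tapering to zero is expressly not a failure under the protocol, but the literal text of 1a removes any remission that follows. The two effects can be neither signed in advance nor assumed to cancel. If the reading of 1a is left open, whoever programs the endpoint chooses it.

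**Working it through.** **1. The rules side by side.** Take a subject on prednisone 20 mg at Day 1, taking the steroid for Crohn's disease.

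| Course during or after taper | Protocol 5.4.3 | SAP Appendix 6 |
|---|---|---|
| Never stopped; 25 mg for 5 days | Failure | Not failure (1b needs 7 days) |
| Never stopped; 25 mg for 10 days | Failure | Failure (1b) |
| Never stopped; raised again to 20 mg or less | Not failure | Not failure |
| Tapered to zero; restarts 10 mg for 10 days | Not failure | Failure if 1a is read literally; not failure if 1a is meant only for subjects not on steroids at Day 1 |
| Tapered to zero; 25 mg for 5 days, then a lower dose to 7 or more days in total | Failure | Failure if 1a is read literally; otherwise not failure |

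Row 1 is a conflict on any reading. Row 4 is a conflict only on the literal text of 1a. The agreement in row 5 rests on that same literal reading.

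**2. Can a subject reach zero and restart before Week 24?** Protocol 5.4.3 tapers prednisone by 2.5 to 5 mg per week; for budesonide, "Subjects who are on budesonide should have their daily dose reduced by 3 mg every 3 weeks". At the highest permitted doses, on nominal days:

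- Prednisone 30 mg at 2.5 mg per week: 30/2.5 = 12 cuts. Zero at Week 21 (first cut at Week 10) or Week 22 (first cut one week later).
- Prednisone 30 mg at 5 mg per week: 6 cuts. Zero at Week 15 or 16.
- Budesonide 9 mg: 3 cuts. Zero at Week 16 (first cut at Week 10) or Week 19 (first cut at Week 13).

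The slowest case leaves 14 nominal days before Week 24. Visit windows (Week 10 ±2 days, Week 24 ±5 days) shorten this: Week 10 on Day 73, first cut on Day 80, zero on Day 80 + 11×7 = Day 157, and Week 24 as early as Day 169 − 5 = Day 164. That leaves 7 days, which only just meets the 7 days in 1a. The missing exemption can therefore matter at every permitted dose on the nominal schedule, with little room in the slowest taper.

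**3. Size per subject.** Inputs: 40 subjects per filgotinib arm, 20 on placebo, and assumed remission of 40% and 20% (SAP 1.3). The plan's own figure reproduces: the Clopper-Pearson 90% interval for 16/40 is 26.9% to 54.2%.

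| Remitters | Rate | 90% exact CI |
|---|---|---|
| 16/40 | 40.0% | 26.9 to 54.2 |
| 15/40 | 37.5% | 24.7 to 51.7 |
| 4/20 | 20.0% | 7.1 to 40.1 |
| 3/20 | 15.0% | 4.2 to 34.4 |

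Each reclassified remitter moves an arm by 1/40 = 2.5 points or 1/20 = 5 points. Neither document names an interval method for the difference, so two are shown. The Wald interval is d ± 1.645·√[p₁(1−p₁)/40 + p₀(1−p₀)/20]. At the assumed rates the standard error is 0.1183 and the half-width 19.5 points.

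| Comparison | Difference (points) | Wald 90% | Newcombe 90% |
|---|---|---|---|
| 16/40 − 4/20 | 20.0 | 0.5 to 39.5 | −1.3 to 36.8 |
| 15/40 − 4/20 | 17.5 | −1.9 to 36.9 | −3.7 to 34.3 |
| 16/40 − 3/20 | 25.0 | 6.7 to 43.3 | 4.2 to 40.7 |

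The 20.0-point difference follows from the two assumed rates; neither document states it as a target.

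**4. How many subjects?** The documents give no rate of Day 1 steroid use or of restarts. Purely as an assumption for the missing exemption, 20% to 50% on steroids at Day 1 and 5% to 20% of those restarting after zero gives 40×0.20×0.05 = 0.4 to 40×0.50×0.20 = 4 subjects per filgotinib arm, and 0.2 to 2 on placebo. Only those who would also be in remission at Week 24 change the result.

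**The case against.** The strongest reply concerns 1a. Appendix 6 separates commencement from escalation above the Day 1 dose, and 1b is plainly the rule written for subjects who have a Day 1 dose. If 1a also caught use at or below baseline in those subjects, the baseline threshold in 1b would do nothing for anyone who had stopped. The SAP says it is based on the protocol, and SAP 6.5 declares no departure on permitted restarts. Item 2 does write a Day 1 exemption for immunomodulators, but it has no escalation rule and so must deal with Day 1 users inside its commencement rule; the comparison is suggestive only.

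This stands as an account of what was probably meant. It does not supply the missing words: 1a covers any steroid at any dose, and a subject who has reached zero can naturally be described as commencing.

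On 1b, one can say that the 7-day threshold is openly stated, is shared with 1a and item 2, and is fixed before unblinding. That is a fair reason to keep it, but not a reason to leave it out of SAP 6.5. Protocol 8.3 leaves missing-data procedures for CDAI, MaRIA and PRO2 to the SAP; it does not hand over the definition of steroid failure, which 5.4.3 states itself.

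Reach is also narrow. Only responders taper. Week 10 non-responders and subjects meeting disease worsening leave blinded treatment. A subject already at the 30 mg or 9 mg cap has no permitted dose above baseline, so the 1b conflict cannot arise within the permitted doses.

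**Conclusion.** Wrong as written, and minor. The 7-day minimum in 1b is a definite, undeclared departure from Protocol 5.4.3 (confidence high). The missing exemption in 1a is a conflict on the literal text, with a plausible but unwritten reading that removes it (confidence moderate).

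The effect is 2.5 points per remitter in a filgotinib arm and 5 points per remitter on placebo, for an unknown and probably small number of subjects. Either one-subject shift lies well inside the 19.5-point half-width. The per-subject figures rest on the SAP's assumed 40% and 20% remission.

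Three stronger readings are tempting, and the documents do not support them:

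- That the SAP deliberately fails restarts the protocol permits. The 1a/1b split points the other way; what is shown is a missing exemption.
- That one subject could overturn the result because the Wald lower limit moves from 0.5 to −1.9. The Newcombe limit is already −1.3 at the assumed rates, and SAP 6.2.2 plans no hypothesis test, so crossing zero decides nothing.
- That a tapered subject always has ample time for a 7-day restart. After visit windows, the slowest taper may leave as few as 7 days.

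**What to change.** Before unblinding:

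1. Add to item 1a: *For a subject on a corticosteroid at Day 1, restarting it, or a systemic equivalent, during or after taper at doses that stay at or below the Day 1 dose is not commencement.* Leave the rest of 1a as it is, so that a new local drug or route, such as a rectal steroid, still counts, and so does a restart that goes above the Day 1 dose and lasts 7 or more days in total.
2. Keep the 7-day threshold in 1b and list it in SAP 6.5 as a change from Protocol 5.4.3.
3. Report the primary endpoint once more as a sensitivity analysis, counting escalation above the Day 1 dose of any duration during or after taper as failure.

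The cost is one clause, one entry in SAP 6.5 and one table. No new data are needed, because Protocol 5.4 already has concomitant medications recorded at each visit. Settling the wording of 1a now also avoids choosing a reading of a primary-endpoint rule after the treatment codes are known.
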